4.11 Discontinuation of Study Treatment, Withdrawal, and Compliance

Discontinuation from the study treatment does not mean discontinuation from the study. The subject will be considered in follow-up, study procedures should still be completed as indicated by the study protocol, and AEs/SAEs will continue to be reported according to this protocol.

In the absence of treatment delays due to adverse events, study treatment/intervention may continue until:

- General or specific changes in the subject's condition renders the subject unacceptable for further treatment in the investigator's judgment.
- An inter-current illness that prevents further treatment administration.
- The subject decides to withdraw from the study.
- The subject has significant noncompliance with the protocol (see below).
- Unacceptable adverse event(s) and/or dose level reduction beyond requirements as detailed in this protocol.
- The clinical need for concomitant therapy that is not permitted in the study.
- Subjects who sign the informed consent form, enroll, and receive the study intervention, but subsequently withdraw, or are withdrawn or discontinued from the study will not be replaced.

Consent Withdrawal

A subject may decide to withdraw from the study at any time. MCWCC CTO will follow their IRB of record's SOPs regarding consent withdrawal.

If a subject intends on withdrawing consent, staff should confirm which of the following options the subject chooses and document the discussion:

- Full consent withdrawal, with no study follow-up.
- Selective consent withdrawal from the interventional portion of the study but agree to continued follow-up of associated clinical outcome information.

Investigator-initiated Withdrawal

The investigator will withdraw a subject whenever continued participation is no longer in the subject's best interests. Reasons for withdrawing a subject include, but are not limited to, disease progression, the occurrence of an adverse event or a concurrent illness, a subject's request to end participation, a subject's noncompliance, or simply significant uncertainty on the part of the investigator that continued participation is prudent. The reason for study withdrawal and the date the subject was removed from the study must be documented.

4.12 Lost to Follow-up

The following actions must be taken if a participant fails to return to the clinic for a required study visit and/or is unable to be reached for follow-up:

- The investigator or designee must make every effort to regain contact and/or reschedule a missed visit with the participant.
- A participant is deemed lost to follow-up if his/her status cannot be obtained after *all* of the following occurs at two consecutive scheduled protocol calendar timepoints:
 - Three telephone calls (at least one day apart) from the study team are unanswered, **AND**
 - A letter (Appendix 2) to the participant's last known mailing address goes unanswered, **AND**
 - These contact attempts must be documented in the participant's medical record or study file.
- Update OnCore® (Follow-up tab and eCRF) when a participant is officially considered lost to follow-up.
- If a subject is considered lost to follow-up, but subsequently contacts the study team, the subject should be considered in follow-up again.

4.13 Accrual Suspension and Closure

The MCW PI facilitates the suspension and closing of accrual in the following manner:

- OnCore® tracks accrual throughout the study.
- If the study must be suspended, OnCore® is updated to “suspended” status.
- When the accrual number is reached, OnCore® notifies staff of study closure.

4.14 End-of-Study Definition

A participant is considered to have completed the study if he or she completed all phases of the study, including the last visit or the last scheduled procedure shown in the calendar of events or has been discontinued.

4.15 Study Discontinuation and Closure

This study may be temporarily suspended or prematurely terminated if there is sufficient reasonable cause (as determined by the MCW study PI, DSMC, sponsor, and/or IRB). Written notification, documenting the reason for study suspension or termination, will be provided by the suspending or terminating party to study participants, investigator, funding agency, the investigational new drug (IND) sponsor, and regulatory authorities. If the study is prematurely terminated or suspended, the MCW principal investigator (PI) will promptly inform the MCW Institutional Review Board (IRB), and the sponsor and will provide the reason(s) for the termination or suspension. Study participants will be contacted, as applicable, and be informed of changes.

5 TREATMENT PLAN

5.1 Study Intervention

The main objective of this study is to provide preliminary evidence that the FDA-approved dose of transdermal buprenorphine in conjunction with oral tramadol can provide adequate analgesia of radiation-induced mucositis pain during treatment and the follow-up period in head and neck

cancer patients. There is no clear consensus definition of adequate pain relief in this setting. For the purpose of our trial, we have defined adequate analgesia as VAS $\leq 3/10$ for 72 hours. Inadequate analgesia is defined as VAS $>3/10$ for 72 hours and unbearable pain as VAS $>3/10$ for 96 hours based on some prior studies and titratability requirements of a TD buprenorphine dose. (16, 17). Patients found to be eligible for the study can be screened and enrolled anytime during first six weeks of radiation therapy. Pain app data monitoring, BPI, base line labs, and medical history as outlined in study calendar will be collected on the day of enrollment. Treatment with study regimen, collection of PROMIS®, MDASI, and other assessment data, as outlined in the study calendar will start once the patient develops mucositis and has a VAS $\geq 4/10$ pain score on the OM Pain App and BPI questionnaire (question 3: your pain at its worst in last 24 hours). Patients usually develop mucositis by the third to fourth of radiation therapy. Therefore, we anticipate treatment would begin by the fourth week in most patients, but it can start sooner if the patient develops mucositis and has VAS $\geq 4/10$ pain. If a patient presents with radiation-induced mucositis pain on the day of enrollment, then all study procedures, including administration of the PROMIS® and MDASI will be completed that day.

The OM Pain App will be installed on their smartphone. Subjects who do not have a smartphone will be provided with a wifi-enabled device with a pre-installed OM Pain App. Treatment with the study regimen will commence once at least grade 1 radiation-related mucositis is observed and mucositis-related pain measured by the visual analog scale (VAS) on BPI questionnaire $\geq (4/10)$ anytime during radiation therapy. Pain scores will be evaluated according to the visual analog scale (VAS), with 0 indicating no pain, 10 indicating the worst pain, 1–3 indicating mild pain, 4–6 indicating moderate pain, and scores ≥ 7 indicating severe pain. Investigators in earlier studies on radiation-induced mucositis pain have used Tylenol®, NSAIDS, and viscous lidocaine to manage mild pain and initiated long-acting pain medications like buprenorphine and fentanyl patch to treat moderate to severe pain. For the study purposes, we decided to start the treatment regimen once radiation mucositis pain $> 4/10$ VAS pain score on the BPI and pain app. The study drug combination, including transdermal buprenorphine 5 mcg to 20 mcg/week with oral tramadol 50 mg to 400 mg/day as needed for breakthrough pain (details in Table 2), will be provided to the study population. Drug will be dispensed by investigators after verifying opioid use information on WIPDMP. Radiation-induced mucositis begins to heal approximately two weeks after the last dose of stomatotoxic chemotherapy or radiation therapy.(30, 32) We will assess a percentage decrease in pain score by the end of week 9 of treatment to show a drug response. This way, we will try to avoid any bias of the normal healing process on pain alleviation. Based on our clinical practice experience and earlier studies, most HN patients will continue to have moderate to severe mucositis pain until 12 weeks of the follow-up period. Thus, we decided to monitor these patients for 12 weeks in our study.(32) Moreover, it would be easier to focus on the side effect profile of the study drug combination after completion of radiation therapy, as both chemotherapy and radiation may confound adverse event assessment of study drug regimen.

We will quantify and evaluate mucositis-related pain through the serial VAS-based pain app and BPI short form during a 12-week period (including first seven weeks of radiation and five weeks of the follow-up period). Real-time pain assessments will be done through the OM Pain App. The pain app will record pain readings up to four times daily. Pain scores will also be recorded through BPI short form questionnaires. The clinical research coordinator or investigator will also record symptom severity and functional assessments through the MD Anderson Symptom Inventory-Head and Neck (MDASI-HN) questionnaires. PROMIS® gastrointestinal and cognitive questionnaires will be used to evaluate gastrointestinal and cognitive side effects of the study regimen. These assessments will be completed during weekly clinic visits as per study calendar.

Study assessments can also be completed virtually through a video/telephone visit during the post-treatment follow-up period (weeks 8–12). Dose titration of pain medications as per study protocol will be made over the telephone by investigators or sub-investigators. Patients will leave a MyChart message on EPIC (electronic medical record) if their pain remains uncontrolled on the prescribed dose of pain medications. These changes will be documented as a telephone encounter in the patient's EMR.

We expect that adequate pain control will be achieved with a titratable dose of the (buprenorphine and tramadol) study regimen throughout the treatment and follow-up period of 12 weeks, using the above-mentioned pain assessment tools. We are planning to use a smartphone application (oral mucositis pain app) designed to permit patients to key in pain severity, using a visual analog 0–10 scale in a real-time setting. Deidentified data collected on each patient's smartphone will be backed up wirelessly to secure cloud storage where the data can be analyzed remotely. The software can generate a time-weighted measure of pain, total area under the pain curve (AUC). It also monitors drug compliance and use of rescue pain medications. Head and neck cancer patients being treated with radiation with or without chemotherapy endure maximum radiation-related toxicities during first seven weeks of treatment. During this period, the pain curve often follows an unpredictable nonlinear pattern; hence, it is difficult to predict peaks and troughs of the pain curve of an individual during radiation. We will study the radiation-induced mucositis pain curve patterns during the therapy and follow-up period. We hypothesize that at least 33% of patients being treated with the drug regimen will have a 30% decrease from the highest baseline mean weekly AUC pain score by end of week 9. Earlier studies have shown that a 30% drop in mean AUC pain score from baseline value was significant and suggestive of drug efficacy.(28, 33).

As noted earlier, radiation-induced mucositis begins to heal approximately two weeks after the last dose of stomatotoxic chemotherapy or radiation therapy.(30, 32) Hence, we will assess a percentage drop in pain score by the end of week 9 of treatment to show a drug response. This way we will be able to avoid any bias of the normal healing process on pain alleviation. Studies have also shown that painful mucositis continues four to five weeks after the termination of radiation therapy. Thus, we plan to continue the study drug regimen up to 12 weeks. (17) (32) Recording of data will cease after 12 weeks, at which time mucositis-related pain symptoms substantially abate in many individuals. Details on buprenorphine and tramadol dose determination and titration are included in Section 5.2 of this protocol. Post-marketing data of buprenorphine, other opioid studies, and clinical experience have shown that around 20 percent of the patients receiving transdermal buprenorphine may have inadequate pain control and require rescue off-protocol pain medications despite being on the highest titratable dose of buprenorphine. Therefore, we have allowed the use of oxycodone in situations where pain is uncontrolled on highest titratable doses of the drug regimen and plan to monitor the use off-protocol pain oxycodone in our study.(17, 34)

Details for the use and logistics of the OM Pain App, as well as the measure of the patient's compliance to the use of the pain app are detailed below. This study will not interfere with or cause adjustments to the standard-of-care treatments each patient will receive as determined by their multidisciplinary team of cancer doctors. To this end, basic treatment descriptions and standards are briefly described as a reference to ensure proper patient selection and to verify that patients observed on the trial will be somewhat homogeneous from a treatment perspective. A short description of possible supportive treatments that could be needed during treatment is also included. All study interventions and treatments will be administered on an outpatient basis.

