Study Design	Single-arm prospective clinical trial to determine the efficacy of transdermal buprenorphine and oral tramadol drug combination in alleviating radiation-induced mucositis pain in head and neck cancer patients during treatment and the follow-up period.
Study Agent	Transdermal buprenorphine with oral tramadol.
Number of Subjects	20
Estimated Time to Complete Enrollment:	Approximately 12 months.

STUDY SCHEMA

STUDY CALENDAR

Procedure	Screening ¹	Weeks During Chemoradiation (± 3 days)						Weeks follow-up period ² (± 3 days)					
		1*	2	3	4	5	6	7	8	9	10	11	12
Study Day/Visit Day													
Informed consent	X												
Baseline medical conditions	X												
WHO grade mucositis [#]	X	X	X	X	X	X	X	X	X	X			X
Oral exam for presence of other causes of mucositis (oral candidiasis, infections, trauma), etc.	X	X	X	X	X	X	X	X	X	X			X
Urine drug screen	X												
CBC with differential	X	X	X	X	X	X	X	X	X	X			X
CMP ³	X	X	X	X	X	X	X	X	X	X			X
Opioid use and nonopioid drug use log ⁴		X	X	X	X	X	X	X	X	X	X	X	X
OM Pain App assessment ⁵	X	X	X	X	X	X	X	X	X	X	X	X	X
Pain app compliance questionnaire		X	X	X	X	X	X	X	X	X	X	X	X
Monitor WI PDMP website for opioid use	X	X	X	X	X	X	X	X	X	X	X	X	X
Medical history/stage of disease	X												
Weight	X	X	X	X	X	X	X	X	X	X	X	X	X
Performance status/ECOG	X												X
PROMIS® GI and cognition scoring ⁶		X	X	X	X	X	X	X	X	X	X	X	X
BPI(Brief Pain Inventory) score	X	X	X	X	X	X	X	X	X	X	X	X	X
MDASI-HN ⁶		X	X	X	X	X	X	X	X	X	X	X	X
Review device usage and proper reporting ⁶		X	X	X	X	X	X	X	X	X	X	X	X

Procedure	Screening ¹	Weeks During Chemoradiation (\pm 3 days)						Weeks follow-up period ² (\pm 3 days)					
		1*	2	3	4	5	6	7	8	9	10	11	12
Study Day/Visit Day													
EKG ⁷	X						X						X
Digital image collection of oral cavity to evaluate mucositis ⁸	X				X				X				X
Record type of caloric intake (normal, soft, liquid, parental/enteral)	X	X	X	X	X	X	X	X	X				X
Report use of IV fluids for hydration	X	X	X	X	X	X	X	X	X				X
Adverse event recording (CTCAE v5)	X	X	X	X	X	X	X	X	X				X
Pregnancy test (HCG) for WOCB	X												

*week 1 starts with the first week of radiation therapy and is continuous without adjustment.
WHO mucositis score will be recorded by the investigators during weekly clinic visits

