4. Record of opioid pain medications, laxatives, and antiemetic use from the patient's drug diary will be copied by investigators on weekly clinic visits. This will commence after starting treatment. a) Patients will document pain and supportive medication use data daily in their diaries but that information will be verified and recorded by investigator/research coordinator during weekly clinic visits in the electronic medical record(EMR). This data is currently being collected in a section of pain app. Patients average weekly VAS pain scores (question 3 of BPI questionnaire) will also be documented in EMR during weekly clinic visits as per standard of care and can be used for study purposes.
5. The Oral Mucositis (OM) Pain App will be evaluated by the study team on a daily basis through a real-time pain assessment tool in the mobile app. Patients can start using the OM Pain App before starting therapy to familiarize themselves with the instrument. b) Pain app readings will be recorded up to four times/day. The daily pain data will be analyzed by the UWM research team on a weekly basis.
6. All questionnaires/forms can be recorded on weekly in-person visits from weeks 1–7 then completed weekly through in-person/telephone interviews by CTO staff from week 8–12. Other assessments can also be done over phone during week 8, 10 and 11. Window period of +/-3 days will be allowed for data collection.
7. EKG will be done at screening and then on week 7 and 12 if the patient is on treatment with Buprenorphine patch.
8. Digital photos will be taken to document mucositis on the day of enrollment, treatment initiation, then during week 9 and week 12 clinic visits.

=

LIST OF ABBREVIATIONS

AE	adverse event
ALP	alkaline phosphatase
ALT	alanine aminotransferase
ANC	absolute neutrophil count
AST	aspartate aminotransferase
AUC	area under the curve
BPI	Brief Pain Inventory
BUN	blood urea nitrogen
CBC	complete blood cell (count)
CDK	cyclin-dependent kinases
CQ	chloroquine
CR	complete response
CRC	clinical research coordinator
CRF	case report form
CSF	cerebral spinal fluid
CT	computerized tomography
CTCAE	Common Terminology Criteria for Adverse Events
CTL	cytotoxic T cell
CTO	Clinical Trials Office
DFS	disease-free survival
DLT	dose-limiting toxicity
DSMC	Data and Safety Monitoring Committee
DSMP	data and safety monitoring plan
ER	estrogen receptor
FDA	Food and Drug Administration
GCP	good clinical practice
GVHD	graft-versus-host disease

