4.1 Subject Status

Subject statuses throughout the trial are defined as follows:

- Prescreening: preconsent (subject considering trial or study staff considering a patient for the trial per institutional recruitment methods).
- Screening: the period after the consent, but prior to eligibility confirmation.
- Consented: consented, prior to eligibility confirmation.
- Eligible: the local investigator confirms all eligibility criteria apply.
- On study/enrolled: date eligibility is confirmed.
- On arm: date of enrollment.
- On treatment: first-day treatment with study drug regimen while undergoing radiation
- Off treatment: last day of treatment with study drug regimen
- On follow-up: from the last day of treatment to the end of the follow-up period.
- Off study: follow-up period completed, with no additional data gathered.

- Withdrawn: subject fully withdraws consent (i.e., refuses ALL follow-up, even survival) or is taken off the study by the local principal investigator.

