5.2 Dose Determination for Buprenorphine and Tramadol

Based on our clinical experience and earlier studies barring exceptions, the typical MEDD dose of standard-of-care regimens, such as oxycodone, morphine and fentanyl patch used in the treatment of radiation-induced mucositis can range from 20 to 90 mg. Buprenorphine is a potent opioid substitute but there is no consensus at equipotency ratio for morphine to transdermal buprenorphine. Some authors have reported that it lies somewhere between 75:1 to 100:1.(34) This makes finding the appropriate morphine equivalent daily dose (MEDD) for buprenorphine in controlling mucositis-related pain a challenging task. For our study, we used 75:1 equipotency ratio to calculate our morphine equivalent daily dose (**Table 1**). As transdermal buprenorphine is a long-acting medication, we plan to allow tramadol 50 mg (total daily dose) as needed for breakthrough pain up to 400 mg/day (total daily dose), which roughly translates to 5 mg to 40 mg MEDD. Steady-state plasma buprenorphine concentration levels are achieved by day 3, during the first application of buprenorphine. Therefore, it can be titrated after a minimum of 72 hours. We hope to evaluate the possibility of using tramadol to facilitate dose adjustment of buprenorphine. With the buprenorphine and tramadol combination, we hope to provide MEDD to patients which is comparable to other standard-of-care opioids. There is no clear consensus definition of adequate and inadequate pain relief in this setting. However, it is well known that a VAS pain score of $\leq 3/10$ is considered mild intensity pain in multiple settings. Based on some earlier studies and the titratability of TD buprenorphine dose, we have defined adequate analgesia as VAS $\leq 3/10$ for 72 hours, inadequate analgesia as VAS $> 3/10$ for 72 hours, and unbearable pain as VAS $> 3/10$ for 96 hours.(16, 17) If patients have unbearable pain (VAS $> 3/10$ x 96 hours) despite being on highest dose of the buprenorphine patch and tramadol, then, we will switch from tramadol to oxycodone for breakthrough pain and continue treatment with buprenorphine. We will titrate this combination as needed for pain control until study completion. Some authors have also shown the benefit and safety of using immediate-release oxycodone in conjunction with transdermal buprenorphine for moderate to severe pain.(35) If the pain is still uncontrolled $> 3/10$ for 72 hours, even after using oxycodone 90 mg/day with buprenorphine 20 μ g/hour, then, the patient will be taken off the study regimen. However, data monitoring will continue. Patients suffering intolerable side effects (severe constipation, vomiting, headache, pruritis, sedation, or respiratory depression, etc.) or those who wish to switch to standard-of-care oxycodone due to ineffective pain control or unclear reasons at any time during the study will be taken off study regimen. However, data monitoring through the pain app and questionnaires will continue. The dose titration schedule is illustrated in **Table 2**.

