6.2.2 Reporting of Adverse Events and Serious Adverse Events

Please refer to Table 3 below to identify adverse events that meet reporting requirements. All serious adverse events (SAEs) that occur after the subject has signed the consent form through 30 days post last dose of study drug(s) will be reported. All SAEs will be followed until satisfactory resolution, or until the investigator deems the event to be chronic. All serious adverse events (SAEs) must also be documented in OnCore®.

Table 3: Adverse Events and Serious Adverse Events Reporting Requirements.

Attribution	SAE				AE		
	Grade 1, 2 & 3		Grade 4 and 5		Grade 3	Grade 4	
	Expected	Unexpected	Expected	Unexpected	Unexpected	Expected	Unexpected
Unrelated Unlikely	IRB ¹ and DSMC- Routine Review ²	IRB ¹ and DSMC- Routine Review ²	IRB ¹ - Routine Review ²	IRB ¹ - Routine Review ² DSMC ³ - Within 5 calendar days	DSMC ² - Routine Review	DSMC ³ - Within 5 calendar days	DSMC ³ - Within 5 calendar days
Possible Probable Definite	IRB ¹ and DSMC ³ - Within 5 calendar days	IRB ¹ and DSMC ³ - Within 5 calendar days	DSMC ³ - Within 5 calendar days	IRB ¹ and DSMC ³ - Within 5 calendar days			

Footnotes

¹ Guidance on adverse event reporting to the IRB will follow the current [MCW IRB Policies and Procedures](#).

² For routine reporting, the events will be reported to IRB as part of the annual continuing progress report, and the DSMC will review events entered in OnCore™ at the time of scheduled monitoring.

³ For expedited DSMC reporting, study coordinator/research nurse must notify the DSMC via email. For AEs, include the subject ID, date of event, grade, relatedness, expectedness, and a short narrative. For SAEs, DSMC will review the SAE report entered into OnCore™.

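### SAEs are reportable through 30 days after the last dose, but no scheduled contact asks about new ones after week 12, when patients may still be on the patch

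*Combined protocol and SAP*

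**What the plan says.** Section 6.2.2 covers SAEs from signed consent "through 30 days post last dose of study drug(s) will be reported". Section 6.2.1 collects AEs from the start of the regimen to the end of follow-up. Both sections follow events already identified until they resolve or, subject to each section's conditions, are judged chronic.

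Dosing may run to the end of the calendar. Section 5.1 states "Thus, we plan to continue the study drug regimen up to 12 weeks". Section 5.2, on buprenorphine with oxycodone for patients with unbearable pain at the top dose, adds "We will titrate this combination as needed for pain control until study completion". Calendar note 7 expects some late patch users: "EKG will be done at screening and then on week 7 and 12 if the patient is on treatment with Buprenorphine patch". In weeks 8 to 12, Table 2 (5.4) tapers only after 72 hours of controlled pain and otherwise allows dose increases.

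Scheduled contact stops at the same point. Clinician visits are in weeks 1 to 7, 9 and 12, with a window of +/-3 days, and the calendar's last adverse event entry is in week 12. Section 5.1 also says "Recording of data will cease after 12 weeks". Section 4.1 gives the final status as "Off study: follow-up period completed, with no additional data gathered".

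**The concern.** The reporting duty is tied to the last dose, while scheduled contact is tied to the start of radiation. The two match only for patients who stop early enough. For a patient dosed late, the plan sets a 30-day window and then schedules nothing that would find a new event in its later part.

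The record could then not distinguish a patient with no late SAE from one who was never asked. That matters in an opioid trial because 6.1.2 lists the development of drug dependency or abuse among its examples of medically important events, and such events may appear around taper and hand-over. Section 8.7 sets no formal stopping rule, so oversight depends on events reaching the monitoring committee. For SAEs related to the regimen, Table 3 generally asks for that within 5 calendar days.

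**Working it through.** The plan states no figure to reproduce here. The check is date arithmetic, with days counted from the start of radiation.

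**Inputs**
- SAE window: last dose + 30 days (6.2.2).
- Last scheduled contact: week 12, day 84, window +/-3 days (calendar).
- Taper: 5 mcg/h per week, from the post-radiation period onward, if pain is controlled (Table 2). The earliest first step is day 50, the first day of week 8.
- Last dose: last day of patch wear or last tramadol dose, whichever is later. This follows 4.1, which defines off treatment by the last day of treatment.
- I read the 12-week limit on the regimen as running from the start of radiation, as the calendar and Table 2 do.

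**Latest last dose with full cover**

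84 - 30 = day 54. A visit at day 81 would move this to day 51, and one at day 87 to day 57.

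**Fastest taper**

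Patch removal day = 50 + 7 x (D/5 - 1), where D is the patch strength in mcg/h. Uncovered days = removal + 30 - contact day, floored at 0.

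| D (mcg/h) | Removal day | Window ends | Uncovered after day 84 | If visit on day 87 | If visit on day 81 |
|---|---|---|---|---|---|
| 5 | 50 | 80 | 0 | 0 | 0 |
| 10 | 57 | 87 | 3 | 0 | 6 |
| 15 | 64 | 94 | 10 | 7 | 13 |
| 20 | 71 | 101 | 17 | 14 | 20 |

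Tramadol does not lengthen these gaps. Cut by 50 mg daily from 400 mg on day 50, it reaches zero on day 57, so the last dose is on day 56 and its window ends on day 86. A patient on 400 mg under Table 2 is also on 20 mcg/h, where the patch already sets day 101.

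**Patch removed on day 84**

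84 + 30 = day 114, so all 30 days (85 to 114) lie after the last scheduled contact.

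**Late start**

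Table 2 needs five 72-hour steps, or 15 days, to reach 20 mcg/h. A start on day 42, the end of the first six weeks, reaches it on day 57. With control shown by day 60, the patch is off on day 60 + 21 = 81 and the window ends on day 111, a gap of 27 days. Starts up to day 32 (32 + 15 + 3 = 50) keep the 17-day figure.

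**Alternative reading of last dose**

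If it meant the last patch application, seven days before removal, the gaps after the fastest taper would be 0, 0, 3 and 10 days.

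**The case against.** The strongest reply is that the reporting duty in 6.2.2 does not depend on the calendar. An SAE that becomes known on day 100 is still reportable. This is one centre, patients come from its own clinics, and admissions may surface in the medical record. That is correct, and it limits the point to active detection. It does not close the gap: no scheduled check after week 12 is written down, and following known events does not find new ones.

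A second reply is pharmacological. With removal on day 71, day 84 is already 13 days later. Using 7.1.2 (halving in 12 hours, then a half-life of about 26 hours), the remaining fraction is about 0.5 x 2^-(300/26), or 0.02%. This fairly tempers the 17-day case. It does not help a patient whose patch comes off at or near day 84, and the 30-day window is the plan's own.

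A reader might also infer more than the documents support:
- *That the safety endpoint is compromised.* AE collection under 6.2.1 ends with follow-up, and the calendar serves that window. The 30-day SAE clause is a separate reporting duty.
- *That about 4 of 20 patients are affected.* Section 5.1 says "around 20 percent of the patients receiving transdermal buprenorphine may have inadequate pain control and require rescue off-protocol pain medications" despite the highest dose. That is an expected rate of rescue use, not of being on the patch late. Some of these patients will stop early, and patients on 10 or 15 mcg/h can also have a gap.
- *That the last dose is undefined.* The off-treatment entry in 4.1 largely settles it as the last day of wear.
- *That patients on the patch at week 12 are left without care.* Section 5.1 caps the regimen at 12 weeks, Table 2 gives a taper, both drugs are commercially available, and 5.4 leaves regimens outside the schedule to the clinician. A hand-over sentence would only clarify.

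**Conclusion.** The mismatch is real and minor. For any last dose after day 54, the plan as written leaves part of its own SAE window without scheduled inquiry: 3, 10 or 17 days after the fastest taper from 10, 15 or 20 mcg/h, and up to 30 days if the patch comes off on day 84. Patients whose last dose is by day 54 are fully covered.

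These figures assume a week 12 visit on day 84, last dose taken as the last day of wear or last tramadol dose, and a 12-week limit counted from the start of radiation. If that limit ran from the first dose instead, dosing could pass week 12 and the gap would be larger. The number of patients affected cannot be derived from the documents, nor can the size or direction of any effect on late SAE counts. The week 9 primary endpoint is untouched.

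**What to change.** 1. Add to the study calendar one telephone safety contact 30 to 37 days after the last dose, for every patient whose last dose is after day 54. State there that the last dose is removal of the last buprenorphine patch or the last tramadol dose, whichever is later. Oxycodone should not set this date, since 5.1 treats it as off-protocol. Record new SAEs, related AEs and current opioid use. The contact should not fall before day 30: a window of 30 +/-3 days would allow a call on day 27 and leave the last three days unasked.
2. In 4.1, let off-study status follow this contact where it is due.
3. In 5.1, limit the statement that recording ceases after 12 weeks to pain, diary and questionnaire data.
4. Optionally, add a sentence saying that a patient still on the patch at the end of week 12 passes to the treating clinician for taper or continued analgesia, with drug and dose recorded.

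The cost is amendment wording, at most 20 calls by existing staff, and about five more weeks of follow-up per late-dosed patient. The latest contact is day 84 + 37 = 121. For a patient starting radiation at month 12, that is 12 + 121/30.4, or about month 16, inside the 18 months in 3.3.
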